13 STUDY SUPPLIES AND DEVICE ACCOUNTABILITY

The investigational study devices will be provided to each site upon study sponsor collection and approval of all required regulatory documentation. The device will be labeled “CAUTION: Investigational Device. Limited by United States Law to Investigational Use” and must be stored in a secure (locked) area under the appropriate storage conditions. Access should be limited to designated study staff only. Device accountability logs will be provided to the site. It is the site’s responsibility to document the receipt (maintain shipping records), disposition (per subject use), transfer (if applicable) and return of all study devices.

All unused or expired investigational devices must be returned to SetPoint Medical in accordance with its Return Material Authorization procedures. Explanted Microregulator and POD can be returned or disposed according to investigator’s institutional procedures for disposal of blood contaminated medical devices.

14 PRIOR AND CONCOMITANT MEDICATION

14.1 Prior RA Medication

Prior use must start from date of RA diagnosis and include all approved for RA biologic and targeted synthetic DMARDs. At a minimum, the year of start and stop must be recorded. The subject's medical record should substantiate the type, dose and duration of usage, as well as reason for stopping.

14.2 Required Background RA Therapy

Each subject must continue a background therapy with at least 1 conventional synthetic DMARD started at least 12 weeks prior and at a stable dose since at least 4 weeks prior to informed consent and until Week 12. Missing up to 2 doses due to COVID-19 vaccination is acceptable, except during the 4 weeks preceding informed consent.

Permitted conventional synthetic DMARDs and their approved for RA dosage are:

- Hydroxychloroquine (200-400 mg/day)
- Leflunomide (10-20 mg/day)
- Methotrexate (10-25 mg/week)
- Sulfasalazine (1,000-3,000 mg/day)

Higher stable doses are allowed if indicated by treating physician. Lower stable doses are allowed if dose limiting toxicity precludes using higher doses. Combinations of oral conventional synthetic DMARDs such as methotrexate and hydroxychloroquine or sulfasalazine are acceptable provided all drugs comprising the combination meet stability requirements. Dose adjustments for management of toxicity of the above medications are allowed and should be documented, along with documentation of the AE which led to the change in the medication.

Risks associated with conventional synthetic DMARDs are identified in the labeling supplied with these drugs and should be reviewed with the subject.

Note: Temporary, perioperative changes in background RA therapy are allowed at the discretion of the Co-PI Rheumatologist and the Co-PI Surgeon to reduce the risk of potential bleeding, infection, or delayed wound healing related to the implant procedure. Such changes are considered standard of care.

All changes in background therapy shall be noted on the Concomitant Medication Log.

14.3 Allowed Medications

The following medications are allowed during study participation:

- Glucocorticoids at the equivalent of \leq 10 mg prednisone daily may be continued at a dose documented to have been stable within 14 days prior to informed consent and until Week 12.
- NSAIDs: over the counter may be continued and those by prescription listed below at the approved dose for RA documented to have been stable within 14 days prior to informed consent and until Week 12:
 - Celecoxib (Celebrex)
 - Diclofenac (Voltaren, Cataflam)
 - Diflunisal (Dolobid)
 - Etodolac (Lodine)
 - Flurbiprofen (Ansaid)
 - Ibuprofen (Motrin)
 - Indomethacin (Indocin)
 - Ketoprofen (Orudis, Oruvail)
 - Ketorolac (Toradol)
 - Meloxicam (Mobic)
 - Nabumetone (Relafen)
 - Naproxen (Anaprox, Naprelan, Naprosyn)
 - Piroxicam (Feldene)
- Mild oral opiates (i.e., acetaminophen-codeine [Tylenol 1, 2, 3], tramadol [Ultram], pentazocine [Talwin], hydrocodone [Vicodin, Lortab]) taken as needed to treat pain. Must not be taken 24 hours prior to RA disease activity assessments.

Note: Mild oral opiates taken on a regular basis to treat pain may be continued at a dose documented to have been stable within 14 days prior to informed consent.

Initiating or changing any of the above listed glucocorticoids, NSAIDs or oral opiates after study entry and until completion of Week 12 assessments is not allowed. Any change must be noted on the Concomitant Medication Log.

Temporary, perioperative changes to any of the above listed medication is allowed at the discretion of the Co-PI Surgeon to reduce the risk of potential bleeding, infection, delayed wound healing, or post-operative pain related to the implant procedure. Such changes are considered standard of care and shall be noted on the Concomitant Medication Log.

14.4 Prohibited Medications and Interventions

The following medication and interventions are prohibited:

- Steroid pulse therapy through completion of Week 12 assessments
- Biologic or targeted synthetic DMARDs through completion of Week 12 assessments
- Intra-articular corticosteroid injection through completion of Week 12 assessments
- Ionic or nonionic linear chelated gadolinium-based contrast agents for MRI studies such as gadodiamide, gadoversemate, gadofosvest trisodium, gadoxetate disodium, gadopentate dimeglumine, and gadobenate dimeglumine

The following interventions are prohibited for subjects with an implanted MicroRegulator:

- External electrical stimulation devices (e.g., TENS units) on the neck
- Electrically active implantable medical devices (e.g., cardiac pacemakers, automatic implantable cardioverter-defibrillators)
- Extra-corporeal shock wave lithotripsy in the cervical spine region
- Short-wave diathermy, microwave diathermy, or therapeutic ultrasound diathermy. Diagnostic ultrasound is not included in this contraindication
- Electrosurgery (electrocautery or radio frequency ablation devices) in the cervical spine region
- Monopolar electrocautery
- Any investigational therapy
- Therapeutic radiation

In the event a subject requires any of the above interventions, MicroRegulator must be suspended (see Section 11.8), decommissioned (see Section 11.9) or explanted (see Section 11.10), as applicable. In the event therapy is suspended or decommissioned, subject should continue to follow the regular visit schedule and adhere to all study procedures and will be followed for safety.

14.5 Rescue Treatment

Additional treatment for RA is only allowed after completion of Week 12 assessments in the event the subject experiences worsening of RA symptoms or if the subject does not experience adequate clinical improvement. If additional RA treatment must be provided prior to Week 12, this is considered rescue treatment and will be reported as a protocol deviation. Not allowing additional treatment until after Week 12 is consistent with contemporaneous drug studies and “FDA’s Draft Guidance for Industry Rheumatoid Arthritis: Developing Drug Products for Treatment (Draft Guidance May 2013)” because it ensures sufficient time for evaluation of clinical response to investigational treatment.

After completion of Week 12 assessments, additional treatment for RA may be provided at any time. The decision about the need, type and timing of treatment is left to the discretion of the Co-PI Rheumatologist and the subject. The Co-PI Rheumatologist will take into consideration in their

CONFIDENTIAL

May not be reproduced outside of SetPoint Medical without written permission from Document Control.

70 of 111

decision the available results from RA disease activity assessments, subject's medical history and information in the labeling of the treatment being considered.

IMPORTANT: The Co-PI Rheumatologist shall discuss with the subject risks associated with the treatment chosen, **particularly any black box warnings included in the label for the prescribed treatment in the context of each subject's medical history and comorbidities**. If there are additional monitoring or testing required to help mitigate such risks, this shall also be discussed with the subject. The Co-PI Rheumatologist shall refer to the Medication Guide Database for current safety information related to the treatment chosen (<https://www.fda.gov/drugs/drug-safety-and-availability/medication-guides>). This information shall be reviewed with the subject and the subject shall be informed that the guide will be provided to them at the pharmacy when the drug is dispensed.

*Note: On September 1, 2021, FDA issued a drug safety communication specific to JAK inhibitors. It is important that the Co-PI Rheumatologist is aware of this information if considering a JAKi for the subject's treatment. This information is provided in **Appendix B** and can also be located at the following website:*

<https://www.fda.gov/drugs/drug-safety-and-availability/fda-requires-warnings-about-increased-risk-serious-heart-related-events-cancer-blood-clots-and-death>

This information shall be provided to the subject if a JAKi is chosen as treatment.

Both the Co-PI Rheumatologist and subject will remain blinded to original treatment assignment when making this treatment decision. Blinding is maintained until the dataset for primary analysis is locked, and the study data are unblinded.

Additional treatments considered as rescue are RA disease modifying drugs that may include, but are not limited to:

- Addition of a biologic or targeted synthetic DMARD
- Dose increase of the ongoing conventional synthetic DMARD background therapy or addition of another conventional synthetic DMARD
- Addition or dose increase of a corticosteroid (equivalent to an average daily use > 10 mg prednisone/day between study visits);
- A corticosteroid injection within 30 days of a study visit.

The need, timing, type and reason for rescue treatment are recorded on the follow-up visit and Concomitant Medication CRFs and entered into the EDC.

Subjects initiating rescue treatment prior to Week 12 will be imputed as non-responders in the analysis of primary and key secondary efficacy endpoints. The initiation of these treatments with study treatment during open-label follow-up is considered "augmented therapy" since it is allowed at the discretion of the Co-PI Rheumatologist and the subject after Week 12. Subjects

treated with augmented therapy will be evaluated as a subgroup for the purpose of exploratory efficacy analysis (see Section 17.7).

Subjects that are rescued or receiving augmented therapy will continue to receive their assigned study treatment unless suspension of stimulation is judged necessary by the Co-PI Rheumatologist and the subject (see Section 11.8).

Subjects that receive rescue treatment or augmented therapy are expected to continue adhering to the study follow-up visit schedule, complete the study procedures, and to be monitored for safety.

15 ASSESSMENT OF SAFETY

15.1 Specifications of Safety Parameters

Adverse events (AEs) for each subject from the time the subject gives written informed consent through Week 264 (end of study) will be recorded in the EDC system and monitored. Each AE will be evaluated by clinical investigators in terms of seriousness, severity (i.e., mild, moderate, severe) and strength of relationship (i.e., not related, unlikely related, probably related, definitely related, indeterminate) to the implant device, implant procedure, explant procedure, Energizer and stimulation therapy. Each AE will be reviewed by sponsor in accordance with sponsor's SOP. The study sponsor is responsible for ensuring that all AEs are appropriately recorded, adjudicated and, when applicable, reported to the government(s), ethics committee(s) and other study centers per applicable regulations. The sponsor will also appoint an independent Data Monitoring Committee (DMC) for ongoing monitoring of subject safety (see Section 18.2.5). Subjects with RA experience a persisting set of symptoms associated with the disease and may continue to present with a wide range of symptoms during the recovery process after the implant procedure. Subjects healing appropriately may suffer from acute infections and/or inflammatory exacerbations unrelated to the procedure due to the natural course of their RA. Therefore, clinical investigators will evaluate the occurrence of AEs, excluding usual post-operative recovery signs and symptoms experienced by study subjects, unless corroborated by objective findings and/or requiring specific medical or therapeutic interventions (e.g., antibiotics).

15.2 Classification of AEs

15.2.1 AE severity

All AEs will be reported from the time of consent through study exit. All AEs will be categorized in terms of their severity as:

- *Mild.* Event results in mild or transient discomfort, not requiring intervention or treatment; does not limit or interfere with daily activities
- *Moderate.* Event is sufficiently discomforting so as to limit or interfere with daily activities; may require interventional treatment

- *Severe.* Event results in significant symptoms that prevents normal daily activities; may require hospitalization or invasive intervention

15.2.2 AE causality

The relationship of all AEs to the implant procedure, explant procedure, implant device, Energizer and stimulation will be evaluated by Co-PIs and categorized as:

- *Definitely related.* There is a clear temporal association, and no other possible cause.
- *Probably related.* There is a clear temporal association, and a potential alternative etiology is not apparent.
- *Unlikely related.* The AE does not follow a reasonable temporal association; or causal relationship with the device or procedure involved in the research is unlikely but cannot be completely ruled out.
- *Not related.* The AE is completely independent of the study investigational device, and/or evidence exists that the event is definitely related to another etiology. There must be an alternative, definitive etiology documented by the investigator.
- *Indeterminate.* Information gathered about the AE is not sufficient to arrive at a definite conclusion about causal relationship.

Any AE that is determined to be definitely related or probably related to the study investigational device or procedure will be categorized as device related. Once the study dataset is locked for primary analysis and the study is unblinded, if a subject was assigned to the control group but has an AE reported as related to stimulation, the AE relationship will be updated to “not related.”

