9 SAFETY EVALUATION

9.1 AE and SAEs

The incidence of AEs and SAEs from informed consent date to Week 12 will be tabulated. Each AE will be evaluated by clinical investigators in terms of seriousness, severity (i.e., mild, moderate, severe) and strength of relationship (i.e., not related, unlikely related, probably related, definitely related, indeterminate) to the implant procedure, implant device, stimulation, Energizer, and explant procedure. Any AE that is determined by a participating investigator to be related (definitely related or probably related) to the implant procedure, implant device, stimulation, Energizer, or explant procedure will be categorized as device related. In unblinded analyses, if the subject was assigned to the control group, but the AE indicates relationship to stimulation, the AE relationship will be updated to "not related."

For all AE tables, a subject reporting the same adverse event more than once will be counted once when calculating the number and percentage of subjects with that particular event. If a subject reports the same AE more than once or has the same AE on multiple occasions, the maximum severity grade and relationship will be presented.

The frequencies and percentages of treatment-emergent adverse events will be presented by MedDRA system organ class (SOC) and preferred term (PT). Complete subject listings of all AE will be provided. For each AE the following will be specified: start and stop dates, severity grade, MedDRA SOC and PT, relationship (not related, unlikely related, probably related, definitely related, or indeterminate) to the implant procedure, implant device, stimulation, Energizer, and explant procedure, , as well as action taken, outcome of the adverse event, and seriousness.

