6 EXPLORATORY EFFICACY ANALYSES

6.1 General Considerations

For each follow-up time point, all dichotomous variables will be reported as responders / patients who have achieved that follow-up duration, percentage of responders, and 95% CI.

Values will be reported at each follow-up timepoint.

For continuous measures, mean, SD, median, minimum and maximum will be presented at each time point.

Time will be measured from initiation of stimulation. Therefore study participants originally randomized to stimulation will, for example, have Week 24 visits represented at 24 weeks of follow-up while study participants randomized to sham will have Week 24 visits represented as 12 weeks, since they will have been on stimulation on for 12 weeks at the Week 24 visit.

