7 SAFETY EVALUATION

7.1 AE and SAEs

The incidence of AEs and SAEs in the safety population (see Section 5.2) will be tabulated through Week 264 (end of study). Each AE will be evaluated by clinical investigators in terms of seriousness, severity (i.e., mild, moderate, severe) and strength of relationship (i.e., not related, unlikely related, probably related, definitely related, indeterminate) to the implant procedure, explant procedure, implant device, stimulation and Energizer. Any AE that is determined by a participating investigator to be related (definitely related or probably related) to the implant procedure, explant procedure, implant device, stimulation or Energizer will be categorized as device related.

For all AE tables, a subject reporting the same adverse event more than once will be counted once when calculating the number and percentage of subjects with that particular event. If a subject reports the same AE more than once or has the same AE on multiple occasions, the maximum severity grade and relationship to the study implant and/or study drug will be presented.

The frequencies and percentages of treatment-emergent adverse events will be presented by MedDRA system organ class (SOC) and preferred term (PT). Complete subject listings of all AE will be provided. For each AE the following will be specified: start and stop dates, severity grade, MedDRA SOC and PT, relationship (unlikely related, probably related, definitely related or indeterminate) to the implant procedure, explant procedure, implant device, stimulation or Energizer , and, as well as action taken, outcome of the adverse event, and seriousness.

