	Events	n (%)	Events	n (%)	Events	n (%)
Implant Device AE by maximum severity [4][5]						
Mild	xx	xx (xx.x%)	xx	xx (xx.x%)	xx	xx (xx.x%)
Moderate	xx	xx (xx.x%)	xx	xx (xx.x%)	xx	xx (xx.x%)
Severe	xx	xx (xx.x%)	xx	xx (xx.x%)	xx	xx (xx.x%)
Stimulation related AE by maximum severity [4][5]						
Mild	xx	xx (xx.x%)	xx	xx (xx.x%)	xx	xx (xx.x%)
Moderate	xx	xx (xx.x%)	xx	xx (xx.x%)	xx	xx (xx.x%)
Severe	xx	xx (xx.x%)	xx	xx (xx.x%)	xx	xx (xx.x%)
Energizer related AE by maximum severity [4][5]						
Mild	xx	xx (xx.x%)	xx	xx (xx.x%)	xx	xx (xx.x%)
Moderate	xx	xx (xx.x%)	xx	xx (xx.x%)	xx	xx (xx.x%)
Severe	xx	xx (xx.x%)	xx	xx (xx.x%)	xx	xx (xx.x%)
Explant Procedure related AE by maximum severity [4][5]						
Mild	xx	xx (xx.x%)	xx	xx (xx.x%)	xx	xx (xx.x%)
Moderate	xx	xx (xx.x%)	xx	xx (xx.x%)	xx	xx (xx.x%)
Severe	xx	xx (xx.x%)	xx	xx (xx.x%)	xx	xx (xx.x%)
SAE [4][5]						
Implant Procedure SAE	xx	xx (xx.x%)	xx	xx (xx.x%)	xx	xx (xx.x%)
Implant Device SAE	xx	xx (xx.x%)	xx	xx (xx.x%)	xx	xx (xx.x%)
Stimulation SAE	xx	xx (xx.x%)	xx	xx (xx.x%)	xx	xx (xx.x%)
Energizer SAE	xx	xx (xx.x%)	xx	xx (xx.x%)	xx	xx (xx.x%)
Explant Procedure SAE	xx	xx (xx.x%)	xx	xx (xx.x%)	xx	xx (xx.x%)

Abbreviations: AE, adverse event; COL, Control to Open Label; SAE, serious adverse event; TOL, Treatment to Open Label

Note: AEs coded using the MedDRA dictionary Version 21.0 or later. Given in the table are subject counts and percentages. At each level of summation, subjects are counted only once. Subjects experiencing AEs of more than one severity are summarized according to the maximum severity experienced over all episodes of an AE

Variable	TOL [1] (N=xxx)		COL [2] (N=xxx)		Safety Population [3] (N=xxx)	
	Events	n (%)	Events	n (%)	Events	n (%)

- [1] Treatment to Open Label (TOL): The TOL population comprises treatment subjects from ITT population who received active stimulation through Week 12, completed Week 12 assessments, continued to receive active stimulation during open-label follow-up, and for whom follow-up data are available.
- [2] Control to Open Label (COL): The COL population comprises control subjects from ITT population who received non-active (sham) stimulation through Week 12, switched to active stimulation after completing Week 12 assessments, continued to receive active stimulation during open-label follow-up, and for whom follow-up data are available.
- [3] Safety population comprises all enrolled subjects.

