Note: AEs coded using the MedDRA dictionary Version 21.0 or later. Given in the table are subject counts and percentages. At each level of summation, subjects are counted only once. Subjects experiencing AEs of more than one severity are summarized according to the maximum severity experienced over all episodes of an AE.

- [1] Treatment to Open Label (TOL): The TOL population comprises treatment subjects from ITT population who received active stimulation through Week 12, completed Week 12 assessments, continued to receive active stimulation during open-label follow-up, and for whom follow-up data are available.
- [2] Control to Open Label (COL): The COL population comprises control subjects from ITT population who received non-active (sham) stimulation through Week 12, switched to active stimulation after completing Week 12 assessments, continued to receive active stimulation during open-label follow-up, and for whom follow-up data are available.
- [3] Safety population comprises all enrolled subjects.
- [4] Percentage calculated based on each analysis population (i.e., TOL, CL, Safety).

Reference: Listing 16.x.x.x

SOURCE: xxxxx SAS 9.4 {program location} {run date/time} }

Table 14.8.3.3
Implant Procedure-Related AEs by SOC and Maximum Severity: All Events

SOC Preferred Term	TOL [1] (N=xxx)				COL [2] (N=xxx)				Safety Population [3] (N=xxx)			
	Mild Events n (%)	Moderate Events n (%)	Severe Events n (%)	Total Events n (%)	Mild Events n (%)	Moderate Events n (%)	Severe Events n (%)	Total Events n (%)	Mild Events n (%)	Moderate Events n (%)	Severe Events n (%)	Total Events n (%)
Any AE [4][5]	xx x (xx%)	xx x (xx%)	xx x (xx%)	xx x (xx%)	xx x (xx%)	xx x (xx%)	xx x (xx%)	xx x (xx%)	xx x (xx%)	xx x (xx%)	xx x (xx%)	xx x (xx%)
SOC 1 [4][5]	xx x (xx%)	xx x (xx%)	xx x (xx%)	xx x (xx%)	xx x (xx%)	xx x (xx%)	xx x (xx%)	xx x (xx%)	xx x (xx%)	xx x (xx%)	xx x (xx%)	xx x (xx%)
Preferred Term 1	xx x (xx%)	xx x (xx%)	xx x (xx%)	xx x (xx%)	xx x (xx%)	xx x (xx%)	xx x (xx%)	xx x (xx%)	xx x (xx%)	xx x (xx%)	xx x (xx%)	xx x (xx%)
Preferred Term 2	xx x (xx%)	xx x (xx%)	xx x (xx%)	xx x (xx%)	xx x (xx%)	xx x (xx%)	xx x (xx%)	xx x (xx%)	xx x (xx%)	xx x (xx%)	xx x (xx%)	xx x (xx%)
Preferred Term 3	xx x (xx%)	xx x (xx%)	xx x (xx%)	xx x (xx%)	xx x (xx%)	xx x (xx%)	xx x (xx%)	xx x (xx%)	xx x (xx%)	xx x (xx%)	xx x (xx%)	xx x (xx%)
Preferred Term 4	xx x (xx%)	xx x (xx%)	xx x (xx%)	xx x (xx%)	xx x (xx%)	xx x (xx%)	xx x (xx%)	xx x (xx%)	xx x (xx%)	xx x (xx%)	xx x (xx%)	xx x (xx%)

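### Protocol 15.2.2 recodes stimulation-related AEs in control-assigned subjects to not related with no onset limit, so as written it also covers AEs arising after crossover to active stimulation

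*Protocol*

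**What the plan says.** Protocol 15.2.2 defines the causality categories and then adds a rule that takes effect once the primary dataset is locked and the study unblinded. It applies to anyone "assigned to the control group but has an AE reported as related to stimulation, the AE relationship will be updated to"; the value substituted is *not related*. The same section says of the *not related* category: "There must be an alternative, definitive etiology documented by the investigator".

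The two SAPs treat this differently.

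- **CLP-004 (Week 12 SAP), section 9.1.** The scope is stated first: "The incidence of AEs and SAEs from informed consent date to Week 12 will be tabulated". The recode follows, restricted to analyses done after unblinding: "if the subject was assigned to the control group, but the AE indicates relationship to stimulation, the AE relationship will be updated to". The value substituted is again *not related*.
- **CLP-008 (long-term SAP), section 7.1.** AEs in the safety population "will be tabulated through Week 264 (end of study"). There is no recode. Tables 14.8.3.1 and 14.8.3.5 report stimulation-related AEs with Treatment to Open Label (TOL), COL and Safety columns. COL subjects are controls who "switched to active stimulation after completing Week 12 assessments, continued to receive active stimulation during open-label follow-up".

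Controls are re-registered to active stimulation after the Week 12 assessments (Protocol 4 and 11.6.1). AEs are collected from consent to Week 264 (Protocol 15.1).

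**The concern.** The protocol rule has two conditions: randomized assignment to control, and a reported relationship to stimulation. Assignment is fixed at Day 0 (Protocol 18.3) and does not change at crossover. Lock and unblinding determine when the update is made, not which AEs it covers. A control who has an AE on active stimulation after crossover therefore meets both conditions.

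For that AE the premise of the rule, that a sham subject cannot have a stimulation effect, is false. The same event on the same active stimulation would count as stimulation-related in a treatment-arm subject and as *not related* in a crossed-over control. Open-label follow-up exists to evaluate long-term safety, and the long-term data available at the time go into the PMA application (Protocol 4). An error of this kind would make stimulation look safer than the investigators reported.

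**Working it through.** **Scope of the rule, place by place**

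| Place | AE window | Recode? | Onset limit on recode? |
|---|---|---|---|
| Protocol 15.2.2 (window in 15.1) | Consent to Week 264 | Yes | None |
| CLP-004 9.1 | Consent to Week 12 | Yes | Implied by the section's scope |
| CLP-008 7.1 | Through Week 264 | No | Not applicable |

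No section of the protocol confines the rule to the sham period. CLP-008 6.1 treats post-crossover control time as time on stimulation, saying of sham subjects that "they will have been on stimulation on for 12 weeks at the Week 24 visit". Protocol 15.2.2 and CLP-008 therefore give different answers for the same AE.

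**What happens to the CLP-008 counts** depends on two things the documents leave open: whether the update overwrites the stored relationship that CLP-008 then reads, and whether it is made once or continuously.

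- Value not carried over: CLP-008 counts are unaffected.
- Carried over, one-time update at lock: COL and Safety-column stimulation-related counts lose the control events on file at lock; later ones survive.
- Carried over, standing rule to Week 264: COL stimulation-related cells are empty and the Safety column is understated.

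**How much exposure is involved** (Protocol 11.11; 1:1 allocation of 240 to 250 subjects, so 120 to 125 controls)

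1. The plan's own duration reproduces: 30 + 21 + 84 + 1,764 = 1,899 days. From Day 0, 84 + 1,764 = 1,848 days = 264 weeks, of which 252 follow crossover.
2. Control share of scheduled active-stimulation time: 252 / (252 + 264) = 252/516 = 48.8%.
3. Planned control time on active stimulation with full follow-up: 120 × 1,764/365.25 = 580 to 125 × 1,764/365.25 = 604 patient-years.
4. Control time already accrued at lock, assuming uniform enrollment, randomization at enrollment and immediate lock. Week 12 is 84/30.44 = 2.76 months, so lock falls at 8 + 6 + 12 + 2.76 = 28.76 months.
   - Stage 1: 30 controls, mean crossover at 4 + 2.76 = 6.76 months, so 22.0 months each; 30 × 22.0/12 = 55.0 patient-years.
   - Stage 2: 90 to 95 controls, mean crossover at 20 + 2.76 = 22.76 months, so 6.0 months each; 90 × 6.0/12 = 45.0 to 95 × 6.0/12 = 47.5 patient-years.
   - Total: 100.0 to 102.5 patient-years, about 17% of step 3 (100.0/580; 102.5/604).
5. Sensitivity. Each month of query resolution and cleaning before lock (CLP-004 4.3) adds 120/12 = 10.0 to 125/12 = 10.4 patient-years. If only 50% to 90% of the time is spent on stimulation (an assumption; Protocol 11.6.1 allows other options after Week 12), the total is 100.0 × 0.5 = 50 to 102.5 × 0.9 = 92.

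Step 4 applies only to the one-time reading. Under a standing rule the relevant exposure is step 3.

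**The case against.** The strongest reply is that nobody would apply the rule after crossover. CLP-004 limits it to Week 12. CLP-008 omits it, although the revision logs of all three documents carry an entry of the same date (29JAN2024) and CLP-008's entry says its AE categorization was aligned with the protocol. CLP-008 7.1 also classes an AE as related when a participating investigator determines it so. On this view the missing words are only a clarification.

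The evidence on intent is good and is accepted here. It does not repair the protocol text, which governs AE classification and states a rule that is wrong for post-crossover events. The investigator-determination wording gives no protection, because CLP-004 9.1 uses the same wording immediately before the recode.

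Three parts of the reply stand.

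- A reader might infer that the COL stimulation-related counts will be zero by construction. That needs both a standing rule and an overwritten value that CLP-008 inherits. Neither is stated, and CLP-004 places its recode at the level of unblinded analyses.
- A reader might project a number of relabelled AEs from the SPM-011 extension study. Protocol 7.3.2 gives two device-related AEs, both in one subject, in a study that included four-times-daily dosing. That cannot support a count, and none is given.
- A reader might infer that safety oversight is impaired. It is not: all-AE rows by class, term and severity stay intact, expedited reporting (Protocol 15.4) is unchanged, and the DMC reviews all AEs and is unblinded.

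**Conclusion.** The point holds as a defect in the wording of Protocol 15.2.2 and a conflict with CLP-008. It should be fixed before the long-term tables are produced. The rule as stated would label AEs on active stimulation *not related* solely because of the Day 0 assignment, although sham-period events are almost certainly what was meant.

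The exposure within reach is 49% of scheduled active-stimulation time, and about 100 to 103 patient-years at lock on the one-time reading. The latter is a planning figure resting on the protocol timeline, uniform enrollment and immediate lock; it is not a bound. The effect on the CLP-008 tables is conditional on the updated value carrying over.

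Two smaller inconsistencies point to the same repair. An automatic recode supplies no documented alternative cause, which 15.2.2 itself requires for *not related*. For adjudicated AEs it sits badly with Protocol 15.3, under which the adjudicator's decision is final for every analysis. No efficacy result is touched.

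Through Week 12, the recode also leaves the control arm with no stimulation-related AEs in the CLP-004 tables. That follows from the intended rule and is a display choice, not part of the error.

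**What to change.** - **Protocol 15.2.2:** limit the recode to the stimulation relationship of AEs with onset before that subject's re-registration to active stimulation. Hold it as a derived analysis flag that leaves the recorded or adjudicated value unchanged, which also removes the tension with 15.3.
- **CLP-008 7.1:** add one sentence saying that stimulation attributions for AEs arising after crossover stand as reported or adjudicated.
- **CLP-004 9.1:** add matching wording on the derived flag; its scope already stops at Week 12.

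The cost is one clause, one sentence, a wording match and one derived variable. Sham-period events are still reclassified in analysis as intended. A table of as-reported, blinded stimulation attributions by arm through Week 12 would be a cheap addition beside CLP-004 Table 14.1.3.5. It is optional and would need a footnote explaining the events in the sham column.
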